**Table 15: Overall Response Criteria**
**Subjects with Target and Nontarget Lesions**

Target Lesions	Non-Target Lesions	New Lesions	Overall Response
CR	CR	No	CR
CR	Non-CR / Non-PD	No	PR
CR	Not evaluated	No	PR
PR	Non-PD or not all evaluated	No	PR
SD	Non-PD or not all evaluated	No	SD
Not evaluated	Non-PD	No	NE
PD	Any	Yes or no	PD
Any	PD	Yes or no	PD
Any	Any	Yes	PD

**Subjects with Nontarget Lesions Only**

Non-Target Lesions	New Lesions	Overall Response
CR	No	CR
Non-CR / Non-PD	No	Non-CR / Non-PD
Not all evaluated	No	NE
Unequivocal PD	Yes or No	PD
Any	Yes	PD

Source: Eisenhauer EA, Therasse P, Bogaerts J, Schwartz LH, Sargent D, Ford R, et al. New response evaluation criteria in solid tumours: revised RECIST guideline (version 1.1). Eur J Cancer 2009;45(2):228-47.

Key: CR = complete response; NE = inevaluable; PD = progressive disease.

Any subject with a CR or PR is to have repeat assessments performed at 4 weeks later to confirm the response.

	Table 2: Derivation of Best Overall Response when confirmation of CR and PR required	18

LIST OF ABBREVIATIONS

Abbreviation	Full Notation
AE	Adverse event
AESI	Adverse event of special interest
ALT	Alanine aminotransferase
AST	Aspartate aminotransferase
ATC	Anatomical Therapeutic Chemical
AUC	Area under the curve
BC	Breast cancer
BMI	Body mass index
CBR	Clinical benefit rate
CI	Confidence interval
C _{max}	Maximum concentration
C _{min}	Minimum concentration
CNS	Central nervous system
CR	Complete response
CSR	Clinical study report
CTCAE	Common Terminology Criteria for Adverse Events
DLT	Dose-limiting toxicity
ECG	Electrocardiogram
ECOG PS	Eastern Cooperative Oncology Group Performance Status
eCRF	Electronic case report form
EOT	End of Treatment
ESR1	Estrogen Receptor 1
FAS	Full analysis set
HR	Hormone receptor
ICH	International Council for Harmonisation
IRC	Independent Review Committee
LDH	Lactate dehydrogenase
MedDRA	Medical Dictionary for Regulatory Activities
MTD	Maximum tolerated dose
NCI	National Cancer Institute

NE	Not evaluable
ORR	Overall response rate
PD	Progressive disease
█	█
PK	Pharmacokinetic(s)
PP	Per protocol
PR	Partial response
PT	Preferred term
QC	Quality control
QD	Quaque die (daily)
QTc	Corrected QT interval
QTcF	Corrected QT interval according to Fridericia's formula
█	█
RECIST	Response Evaluation Criteria in Solid Tumors
RP2D	Recommended Phase 2 dose
SAE	Serious adverse event
SAP	Statistical analysis plan
SD	Stable disease
SOC	System organ class
t _{1/2}	Half-life
TEAE	Treatment-emergent adverse event
TLFs	Tables, listings, and figures
T _{max}	Time to maximum concentration
█	█
ULN	Upper limit of normal range
WHO	World Health Organization

1. INTRODUCTION

This document outlines the statistical methods to be implemented during the analyses of data collected within the scope of Olema Pharmaceuticals, Inc. protocol OP-1250-001 (A Phase I Dose Escalation and Dose Expansion and Phase II Monotherapy Open-label, First-in-Human, Multicenter Study of OP-1250 in Adult Subjects with Advanced and/or Metastatic Hormone Receptor (HR)-Positive, HER2-Negative Breast Cancer (BC)). The purpose of this plan is to provide specific guidelines from which the statistical analyses will proceed. Any deviations from this plan will be documented in the clinical study report (CSR).

2. STUDY OBJECTIVES

Phase I (Dose Escalation Part A and Expansion Part B)

2.1 Primary Objectives

- To identify the dose-limiting toxicity (DLT), maximum tolerated dose (MTD) and/or recommended Phase 2 dose (RP2D) of OP-1250 (Part A).
- To confirm the RP2D of OP-1250 (Part B).
- To assess the safety and tolerability of OP-1250 (Parts A and B).
- To assess the pharmacokinetics (PK) of OP-1250 (Parts A and B).

2.2 Secondary Objectives (Parts A and B)

- To estimate the overall response rate (ORR) defined as the complete response (CR) + partial response (PR) rate of OP-1250.
- To estimate the clinical benefit rate (CBR) (CR+PR + stable disease (SD) \geq 24 weeks) of OP-1250.

█ [REDACTED]

█ [REDACTED]

█ [REDACTED]

█ [REDACTED]

█ [REDACTED]

█ [REDACTED]

Phase II

2.4 Primary Objectives

- To estimate the ORR of OP-1250 in subjects with HR+/HER2- metastatic or locally advanced BC-with no evidence of central nervous system (CNS) metastases who have progressed following at least 1 hormonal therapy regimen in the metastatic or locally advanced setting.
- To assess the safety and tolerability of OP-1250.
- To assess the plasma PK profile of OP-1250.

2.5 Secondary Objectives

- To estimate the CBR of OP-1250 in subjects with HR+/HER2- metastatic or locally advanced BC with no evidence of CNS metastases who have progressed after receiving at least 1 hormonal treatment regimen in the metastatic or locally advanced setting.

[REDACTED]

[REDACTED]

[REDACTED]

[REDACTED]

[REDACTED]

[REDACTED]

[REDACTED]

[REDACTED]

[REDACTED]

3. STUDY ENDPOINTS

The study endpoints of each of the 2 phases of the study are:

Phase I (Dose Escalation and Expansion)

Primary Endpoints:

- Incidence and nature of DLTs as defined in the protocol.
- MTD and/or RP2D of OP-1250 when used as a single agent.
- Incidence, nature, and severity of treatment-emergent Adverse Events (TEAEs) and serious adverse events (SAEs) according to NCI-CTCAE version 5.0.
- Plasma levels of OP-1250 at pre-defined intervals to establish PK parameters (includes maximum concentration (C_{max}), minimum concentration (C_{min}), time to maximum concentration (T_{max}), area under the curve (AUC), half-life (t_{1/2}), and OP-1250 trough concentration at steady state).

Secondary Endpoints:

- ORR by evaluation of tumor response assessments using RECIST 1.1 in subjects with measurable disease.
- CBR as defined by percent of subjects with CR + PR + SD \geq 24 weeks, by evaluation of tumor response assessments using RECIST 1.1.

• [REDACTED]

[REDACTED]

- [REDACTED]
- [REDACTED]
- [REDACTED]
- [REDACTED]
- [REDACTED]
- [REDACTED]

Phase II

Primary Endpoints:

- ORR by evaluation of tumor response assessments using RECIST 1.1 in subjects without evidence of CNS metastases who have measurable disease.
- Incidence, nature, and severity of TEAEs and SAEs according to National Cancer Institute-Common Terminology Criteria for Adverse Events (NCI-CTCAE) version 5.0.
- Plasma levels of OP-1250 at pre-defined intervals to establish PK parameters (includes C_{max}, C_{min}, T_{max}, AUC, t_{1/2}, and OP-1250 trough concentration at steady state). The results of those analyses will be reported separately in PK report.

Secondary Endpoints:

- CBR as defined by percent of subjects with a CR + PR + SD for ≥ 24 weeks, by evaluation of tumor response assessments using RECIST 1.1 in subjects without evidence of CNS metastases.

█

████████████████████

█

█

█

█

█

█

█

█

█

█

4. STUDY DESIGN AND PLAN

This is a Phase I dose escalation, dose expansion and Phase II open-label, first-in-human study to determine the DLT, MTD, and/or RP2D, to characterize the safety and PK profile, and to estimate the preliminary anti-tumor activity of OP-1250 as a single agent in adult subjects with Hormone Receptor positive (HR+)/Human epidermal growth factor receptor 2 negative (HER2-) metastatic or locally advanced BC. Treatment and study subject evaluation will be performed in 28-day cycles. In the absence of unacceptable OP-1250 treatment-related toxicity or disease progression, subjects may receive OP-1250 treatment for up to 1 year at the discretion of the Investigator and beyond 1 year with the agreement of the Investigator and the Sponsor.

Radiographic and/or physical assessments of the malignancy will be made at screening/baseline (within 28 days before the first study drug administration) and after every 2 cycles of treatment. Subjects who have been determined to have obtained a clinical benefit from OP-1250 may decrease the frequency of radiographic and physical assessments of malignancy to every 3 months after the Cycle 8 radiographic assessment. Tumor response will be assessed using RECIST 1.1.

This study comprises 2 Phases: Phase I (Part A and Part B), and Phase II.

Phase I

The rolling 6 dose escalation rules will be employed, considering DLTs observed in Cycle 1. Cohorts of 3 to 6 subjects will be treated at each dose level.

At the end of Phase I, Part A, a comprehensive review of safety, tolerability, and PK data will be performed to assess whether one OP-1250 dose can be identified as the Recommended Phase 2 Dose (RP2D). If this comprehensive review is equivocal on two OP-1250 doses as the possible RP2D, then these two doses will be investigated in Phase I, Part B.

Part B (Dose Expansion)

If one dose is clearly identified during dose escalation in Phase I, Part A as the RP2D, then approximately 30 additional subjects will be enrolled at this dose. If two OP-1250 doses are advanced from Phase I, Part A, then each dose will enroll approximately 30 additional subjects, for a total of approximately 60 subjects.

At the end of Phase I, Part B, a comprehensive review of safety, tolerability, PK and preliminary antitumor activity data will be performed. If only one dose was advanced from Phase I, Part A, i.e., a RP2D was already identified, then the purpose of this comprehensive review will be to assess a preliminary risk:benefit ratio to enable safe enrollment of additional subjects in the Phase II. If two doses

are advanced from Phase I, Part A, then the purpose of this comprehensive review will be 2-fold: first, to select the RP2D, and second, to assess a preliminary risk:benefit ratio of the RP2D to enable safe enrollment of additional subjects in the Phase II, Expansion part of the study.

Phase II

This portion of the study further explores the clinical activity, safety and PK of OP-1250 monotherapy at the RP2D and estimates the preliminary anti-tumor activity. Up to 80 evaluable subjects will be enrolled over 3 cohorts in Phase II as follows:

- Cohort A will enroll approximately 50 subjects with measurable disease without evidence of CNS metastases.
- Cohort B will enroll approximately 15 subjects with non-measurable (evaluable) disease without evidence of CNS metastases.
- Cohort C will enroll up to 15 subjects with CNS metastases.

Additional subjects may be enrolled to allow for subject drop-out. To allow for subject replacement, up to 88 subjects may be enrolled in the Phase II portion of the study.

5. DETERMINATION OF SAMPLE SIZE

5.1 Phase I (Part A Dose Escalation)

For Phase I, Part A, cohorts of 3 to 6 subjects will be enrolled in each OP-1250 dose cohort based on a rolling 6 dose escalation scheme. Each subject will participate in only 1 dose cohort. The total number of subjects to be enrolled in the dose escalation phase of the study is dependent upon the observed safety profile, which will determine the number of subjects per dose cohort, as well as the number of dose escalations required to achieve the MTD. Approximately up to 42 subjects will participate in Phase I, Part A dose escalation.

5.2 Phase I (Part B Dose Expansion)

Up to approximately 60 subjects with measurable disease will participate in Phase I, Part B dose expansion. If 1 dose is clearly identified during dose escalation in Phase I Part A as the RP2D, then 30 subjects will be enrolled at this dose. If 2 OP-1250 doses are advanced from Phase I, Part A, then each dose will enroll approximately 30 subjects for a total of up to approximately 60 subjects.

A sample size of 30 subjects per dose group will provide an estimation precision of $\pm 19\%$ per dose group for any binary event rate assessing safety, tolerability, anti-tumor activity (e.g., overall response, clinical

benefit) or exposure/kinetics. This level of precision is regarded as clinically sufficient in the comprehensive review of safety, tolerability, PK and preliminary anti-tumor activity data to gate enrollment into the Phase II part of the study.

5.3 Phase II

Approximately a total of 80 additional subjects will be enrolled in the expansion phase: 50 subjects in Cohort A, 15 in Cohort B, and 15 in Cohort C. Subjects not evaluable may be replaced.

For the statistical analyses of ORR, data from the 50 subjects in Cohort A who were dosed at the RP2D will be included. A sample size of 50 subjects will provide an estimation precision of $\pm 15\%$ for any binary event assessing safety (e.g., any SAE's) or anti-tumor activity (e.g., overall response, clinical benefit). This level of precision is regarded as clinically sufficient in the preliminary estimation of the risk:benefit profile to plan future clinical trials for OP-1250's clinical development plan.

Subjects without measurable disease are being enrolled in the Phase II study (Cohort B) in order to mimic the general population of ER+ breast cancer subjects, many of which have bone only disease. Subjects without measurable disease in the Phase II are limited to a total of 15 subjects and will not be included in the determination of ORR; however, they will be included in safety, secondary, and exploratory analyses where appropriate [REDACTED]

[REDACTED]

6. GENERAL ANALYSIS CONSIDERATIONS

6.1 Statistical Analysis Cohorts

Statistical analysis will be conducted in the cohorts below.

1. Dose Escalation subjects: All endpoints [REDACTED] will be summarized by dose groups.
2. Subjects treated at 60 mg or 120 mg pooled from dose escalation, dose expansion and phase II (without cohort C): The study subjects and demographic, pharmacodynamic endpoints, and efficacy endpoints will be analyzed by dose groups.

- [REDACTED]
4. All subjects: All safety related endpoints will be summarized based on the safety analysis set by dose groups, [REDACTED] and overall.

For summary by dose groups, the dose groups will be based on the first doses the subjects received.

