### 8.8.4 Recommended Phase II Dose

Following Phase 1a dose escalation of OP-1250 from 30 mg to 300 mg QD, a recommended phase 2 dose (RP2D) range was defined of 60 to 120 mg QD. Sixty patients are planned for Phase 1b enrollment, with 30 patients at each dose level (60 and 120 mg). At 60 mg and 120 mg, OP-1250 demonstrated high oral bioavailability and dose proportional exposure. At 120 mg, OP-1250 consistently exceeded the predicted efficacy plasma concentration thresholds from preclinical models. Safety data from 37 patients enrolled in Phase 1b indicated no clinically meaningful difference in the frequency of TEAEs between the 2 dose levels (60 mg,

120 mg) as the most common TEAEs ( $\geq 10\%$ ) were nausea (28%, 21%), vomiting (17%, 16%), fatigue (17%, 5%), and headache (11%, 11%), respectively. Most events were Grade 1 or 2, with the exception of two Grade 3 events at 60 mg (diarrhea and anemia). There were no dose reductions or discontinuations due to an AE. Based on safety and pharmacokinetic data from Study OP-1250-001, 120 mg OP1250 QD has been selected as the RP2D.

Since the RP2D has been determined, active subjects enrolled on the Phase I part of the study may be treated at the RP2D with approval of the Medical Monitor if the investigator or designee considers this in the best interest of the subject.

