8.2 Safety Analysis Set

The safety analysis set (SAF) will include all subjects who received at least 1 full or partial dose of OP-1250. Subjects will be analyzed according to the OP-1250 doses they actually received as a first dose. The safety analysis set will be used for all safety analyses except for the analyses of DLTs.

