13.2 Adverse Events

Adverse events will be collected from the time of signing of the informed consent until 30 days following the last dose of study treatment or until resolution/stabilization of any ongoing drug related AEs.

All AE summaries will be restricted to TEAEs, which are defined as those AEs with onset or worsening after the first administration of study drug till the 30 days following the last dose of study drug or any study drug related AEs. [Appendix A](#) contains rules for how partial dates will be handled. If it cannot be determined whether the AE is treatment emergent due to a partial onset date, then it will be counted as such. Verbatim terms in the eCRFs will be mapped to (PT and SOC using MedDRA. Adverse events will be assigned a severity grade per NCI-CTCAE version 5.0. For summaries of maximum CTCAE grade, at each level of subject summarization, a subject is classified according to the highest grade if the subject reported 1 or more events. For summaries of TEAEs that are related to OP-1250, a TEAE is considered related to OP-1250 if it is reported by the Investigator as related, probably related, or possibly related.

AE summaries will be presented by OP-1250 dose using SAF set. Summaries that are displayed by SOC and PTs will be ordered by descending frequency of the total column by SOC and by descending frequency of PT within SOC. Summaries of the following types will be presented:

- Overall summary of TEAEs that contain an overview of each item below.
- Subject incidence of DLTs and total number of unique DLTs by MedDRA SOC and PT in the DLT evaluable analysis set.
- Subject incidence of TEAEs and total number of unique TEAEs by MedDRA SOC and PT.
- Subject incidence of grade 3 or greater TEAEs and total number of unique grade 3 or greater TEAEs by MedDRA SOC and PT.
- Subject incidence of OP-1250-related TEAEs and total number of unique OP-1250-related TEAEs by MedDRA SOC and PT.
- Subject incidence of grade 3 or greater OP-1250-related TEAEs and total number of unique grade 3 or greater OP-1250-related TEAEs by MedDRA SOC and PT.
- Subject incidence of TEAEs by MedDRA SOC, PT, and maximum CTCAE grade.
- Subject incidence of serious TEAEs and total number of unique serious TEAEs by MedDRA SOC and PT.
- Subject incidence of OP-1250-related serious TEAEs and total number of unique OP-1250-related serious TEAEs by MedDRA SOC and PT.
- Subject incidence of TEAEs leading to death as an outcome by MedDRA SOC and PT.

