13.3 Extent of Exposure

The analysis will be conducted using SAF set.

Study drug exposure will be summarized using the total number of doses received, total number of cycles, duration of study treatment, relative dose intensity, number of dose interruption, and number of dose reduction. Duration of treatment in weeks is defined as the (last dose date - the first dose date + 1)/7. Relative dose intensity will be calculated as the total amount of dose received divided by (the duration on treatment (in days) × assigned dose). The number of subjects with dose interruption, dose reduction and the reason of dose interruption, dose reduction, the number of dose interruptions and dose reductions will be summarized by frequencies and percentages.

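### By-dose summaries follow the first dose only, so data gathered after a Phase I subject moves to 120 mg stay in the starting-dose column, and relative dose intensity is undefined for that subject

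*SAP*

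**What the plan says.** **Grouping rule.** SAP 6.1 sets one rule for every summary by dose: "For summary by dose groups, the dose groups will be based on the first doses the subjects received". SAP 8.2 repeats it for the safety set: "Subjects will be analyzed according to the OP-1250 doses they actually received as a first dose".

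**Tables that inherit it.** For safety, SAP 6.1 says "All safety related endpoints will be summarized based on the safety analysis set by dose groups", and SAP 13.2 adds "AE summaries will be presented by OP-1250 dose using SAF set". For subjects at 60 or 120 mg, pooled over escalation, expansion and Phase II without Cohort C, SAP 6.1 says "The study subjects and demographic, pharmacodynamic endpoints, and efficacy endpoints will be analyzed by dose groups".

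**Dose change allowed.** Protocol 8.8.4 names 120 mg once daily as the RP2D and continues: "Since the RP2D has been determined, active subjects enrolled on the Phase I part of the study may be treated at the RP2D", subject to Medical Monitor approval. The same section reports that escalation ran from 30 to 300 mg and that 30 subjects were planned at 60 mg in Part B. The bar on raising a subject's dose in Protocol 8.8.1.2 applies only during Part A.

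**Exposure.** SAP 13.3 says: "Relative dose intensity will be calculated as the total amount of dose received divided by (the duration on treatment (in days) × assigned dose". It does not say what the assigned dose is for a subject whose dose is changed to the RP2D.

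**The concern.** A subject who starts at 60 mg and later takes 120 mg contributes person-time at two doses, but the tables have room for only one. Everything recorded after the switch goes to the dose no longer being taken.

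Safety is a primary endpoint in both phases, and the 60 and 120 mg columns will be read side by side. Protocol 6.7 reports four grade 4 neutropenia events in Phase Ia, and Protocol 9.2 makes such events of special interest, so the dose at onset is what a reader will want to know. If risk or activity rises with dose, placing 120 mg data under 60 mg draws the columns together. The 120 mg column also loses the switchers' experience at that dose. For subjects moved down from above 120 mg, the higher-dose column collects events and responses that arose at 120 mg.

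**Working it through.** The plan states no figure on this point, so there is none to reproduce. The check has three steps.

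**1. Does any outcome window close at a switch?**

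| Outcome | Window in the SAP | Ends at a switch? |
|---|---|---|
| TEAEs (13.2) | first dose to 30 days after last dose | no |
| Laboratory shifts (13.4) | worst post-baseline grade | no |
| QTcF (13.6) | post-baseline maximum | no |
| Best response (10.1) | all time points up to first PD | no |
| CBR (10.1) | total time on treatment from first dose | no |
| DLT (13.1) | Cycle 1 | not applicable; no dose increase in Part A |

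With the first-dose rule, every row except the last carries post-switch data into the starting-dose column.

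**2. How many subjects could be misplaced?** The documents do not give the number of switchers, so this is an assumed range. Let *k* of 30 subjects in the 60 mg column switch, and let a share *q* of them have their first event of a given type only at 120 mg. The 60 mg percentage then contains 100 × *k* × *q* / 30 points from events at 120 mg.

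| *k* | *q* = 10% | *q* = 20% | *q* = 30% |
|---|---|---|---|
| 3 | 1.0 | 2.0 | 3.0 |
| 10 | 3.3 | 6.7 | 10.0 |
| 15 | 5.0 | 10.0 | 15.0 |

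These points measure misplacement, not bias. Some of these events might also have occurred had the subject stayed at 60 mg.

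**3. What happens to relative dose intensity (RDI)?** Let *d* be the first dose and *f* the share of treatment days at 120 mg, with full adherence. If the assigned dose is the first dose:

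RDI = [*d*(1 − *f*) + 120*f*] / *d*

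| First dose | *f* = 0.1 | *f* = 0.5 | *f* = 0.9 |
|---|---|---|---|
| 30 mg | 130% | 250% | 370% |
| 60 mg | 110% | 150% | 190% |
| 210 mg | 96% | 79% | 61% |
| 300 mg | 94% | 70% | 46% |

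Example: 168 days at 60 mg and 168 days at 120 mg give 10,080 + 20,160 = 30,240 mg. Divided by 336 × 60 = 20,160 mg, this is 150%. At *f* = 0.5, adherence would have to fall to 60/90 = 67% (from 60 mg) or 30/75 = 40% (from 30 mg) before RDI dropped to 100%. Missed doses are then hidden in subjects moved up, and a fully adherent subject moved down looks under-dosed.

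If the assigned dose is instead the dose assigned on each day, the denominator in the example is also 30,240 mg and RDI is 100%, as it is from any starting dose.

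**The case against.** Grouping by starting dose is a usual primary display. It avoids assigning subjects by something that happens after baseline, and it keeps switchers from lower doses out of the 120 mg column. That stands, and it is why the first-dose tables should remain.

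A reader might infer that the rule undermines the choice of 120 mg. It does not. Protocol 8.8.4 records that choice as already made, on PK and safety data that included 37 Part B patients, and permits switching only afterwards. The Phase II ORR rests on Cohort A subjects dosed at the RP2D (SAP 5.3), and the DLT and MTD results rest on Cycle 1.

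A reader might also infer that a real dose effect is being hidden. The documents show no such gradient. Protocol 8.8.4 reports no clinically meaningful difference in TEAE frequency between 60 and 120 mg, and its two Grade 3 events were both at 60 mg. Those data are early and few, so they do not exclude a gradient, but its direction cannot be assumed.

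The effect on ORR is narrow. Progression ends treatment (Protocol 8.11), and assessments after first PD are not used (SAP 10.1). Only a subject who has neither progressed nor responded by the switch, and then responds, can change the starting-dose ORR.

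Parts of SAP 6.1, 10 and 11 are blacked out and may hold a switch rule. Even so, the visible sentence in 6.1 covers every by-dose summary without exception. The exposure–response and concentration–QT work mentioned in the protocol uses measured exposure, but it does not replace the by-dose tables.

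**Conclusion.** The point holds as a reporting defect that should be corrected. A stated rule, combined with a permitted dose change, puts post-switch safety and response data in a column for a dose the subject was no longer taking, in both directions. What is at risk is the clarity of the final descriptive dose comparison. The size cannot be derived from the documents: under the assumed range of 3 to 15 switchers among 30 and 10% to 30% with a first event only at 120 mg, 1 to 15 points of a 60 mg event rate would come from 120 mg.

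It would go too far to say that switchers will be reported above 100% RDI. That follows only if the assigned dose means the first dose. The first-dose grouping makes this reading natural, but the SAP does not state it, and the other reading gives 100%. The certain defect is an undefined term whose two readings differ by 50 points or more for a 60 or 30 mg starter with half the days at 120 mg.

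Whether any subject should change dose is a clinical matter and is not judged here.

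**What to change.** Keep the first-dose tables as primary, and add to the SAP:

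- **Safety:** supplementary AE, laboratory and ECG tables by dose at onset or assessment, with a separate column for data after a switch to the RP2D.
- **Response:** a flag for responses first documented after a switch, and an ORR sensitivity analysis that does not credit them to the starting dose.
- **Listing:** all switchers, with starting dose and switch date.
- **RDI:** a denominator equal to the sum of the daily assigned doses, updated at a switch to the RP2D but not at toxicity reductions, so that reductions still lower the figure.

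Cutting the primary tables at the switch is not advised. Switchers are selected for still being on treatment, and a subject switched before 24 weeks could not reach the CBR duration at the starting dose.

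The cost is SAP wording and a few extra tables from dosing dates already needed for the exposure analysis. The post-switch column will describe a selected group, and effects of the earlier dose may carry over given the long half-life seen in animals (Protocol 6.2). It should carry a footnote saying so.
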